7.5.3.4 Analysis Methods

For each subject, the VVI pacing control period will occur shortly following investigational software download during the approximately 20-minute algorithm auto-setup phase where the MARVEL 2 programmable parameters are setup to enable optimal tracking of the A4 signal. The auto-setup phase will occur while the MARVEL 2 features are in monitor mode (i.e. VDI pacing which is effectively VVI pacing). For purposes of evaluating the primary efficacy objective, the 20-minute resting period while the MARVEL 2 features are programmed to adaptive mode and providing VDD pacing will serve as each subject's treatment period.

Note that a randomized crossover design will *not* be used to compare AV synchronous pacing percentage between the MARVEL 2 pacing mode and VVI pacing for the following reasons: 1) knowledge of pacing mode is unlikely to influence AV synchronous pacing rate as such knowledge is unlikely to influence right atrial contractility, 2) the auto-setup phase will provide an opportunity to assess the AV synchronous pacing percentage during VVI pacing, 3) carryover effects are not possible since as soon as the MARVEL 2 features are programmed to adaptive mode atrial tracking will commence.

The accuracy spreadsheet derived from each Holter file (see section 7.5.2.3) will be used to determine the synchrony status (yes or no) for each P-wave. Each accuracy spreadsheet will be imported into SAS and/or R and the P-P interval computed for each P wave i (where $i > 1$) as the time in seconds in Column 1 (A) for the i^{th} P-wave minus the time in seconds in Column 1 (A) for the $i^{\text{th}}-1$ P-wave. Each P-wave in the accuracy spreadsheet file will be classified as being evaluable or not evaluable. P-waves that are not evaluable include:

1. P-waves with no ventricular sense or pace markers and indication of telemetry dropout in the first 300 ms after the P-wave. These are identified from the accuracy spreadsheet where column 13 (M) = 0 and column 14 (N) = 1.

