2. P-waves that occur during an AV conduction mode switch as these P-waves occur when the pacing mode is set temporarily to VDI40 while the device checks for intrinsic AV conduction. These are identified from the accuracy spreadsheet where a supplemental marker in the preceding P-P interval (column 15 (O) < P-P interval), and the pacing mode in the supplemental marker is VDI40, indicating a mode switch (column 17 (Q) = 7). Note that for the pacing mode, the supplemental marker indicates the pacing mode on the next ventricular event, which is why a look-back to the preceding supplemental marker is necessary to determine if the current ventricular event is in a mode-switched state.

All other P-waves in the accuracy spreadsheet will be considered evaluable. Evaluable P-waves will be considered synchronous if they occur within 300 ms of the following ventricular event. Thus, evaluable P-waves will be considered synchronous if column 2 (B) < 0.3 and asynchronous if column 2 (B) \geq 0.3.

For the analysis of the primary efficacy objective, P-waves with records in the accuracy spreadsheet corresponding to the auto setup phase (i.e. columns 11 (K) and 12 (L) indicate auto setup phase) or

resting phase (i.e. columns 11 (K) and 12 (L) indicate auto setup phase) will be selected. The auto setup phase will occur during MARVEL 2 monitor mode pacing (i.e. VVI pacing) and the resting phase will occur during MARVEL 2 adaptive mode pacing (i.e. VDD pacing). If at least 70% of evaluable beats are considered synchronous during the VVI or MARVEL 2 adaptive pacing mode during resting, then the subject will be considered to have met the primary efficacy endpoint during the VVI or MARVEL 2 adaptive pacing mode during rest respectively. McNemar's test for paired proportions will be used to test the primary efficacy objective hypothesis. Note that subjects with fewer than 500 evaluable beats during each period will be excluded from the primary efficacy analysis.

[REDACTED]

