7.5.4.4 Analysis Methods

All available Holter recordings (including multiple recordings for subjects evaluated at multiple visits following initial Micra implant) will be used to determine if a subject meets the primary safety endpoint. The ventricular event spreadsheet derived from each Holter file (see section 7.5.2.4) will be used to determine the primary event status associated with each Holter recording. Each ventricular event spreadsheet will be imported into SAS and/or R.

The MARVEL 2 features will be considered enabled when column 6 (F) in the ventricular event spreadsheet has the values 5, 6, 7, or 14.

Next, the ventricular markers from the Micra device will be searched for long intervals. To accomplish this, the programmed lower rate interval will be computed by converting column 3 (C) to seconds by dividing 60 by the value in column 3 (C). Next, the difference in seconds between the current ventricular event and the next ventricular event will be calculated (i.e. the V-V interval). If this value exceeds twice the programmed lower rate interval and there is no telemetry dropout (i.e. column 4 (K) = 0) the event will be flagged for further investigation.

Similarly, the ventricular rate in seconds from one ventricular event to the next will be calculated and used to determine if the rate exceeds 100 bpm (0.6 seconds). If the time from the first ventricular event with a rate exceeding 100 bpm to the last ventricular event with a rate exceeding 100 bpm is greater than 3 minutes, the sequence of events will be marked for further investigation. Note that the ventricular rate associated with ventricular events where there is evidence of telemetry dropout (i.e. column 4 (K) = 1) will not be computed and the ventricular event will be ignored when computing the duration of rates exceeding 100 bpm. This strategy makes the implicit assumption that the higher rate continues through the telemetry dropout period unless the next pair of ventricular events has a rate

below 100 bpm. The telemetry protocol between the implanted Micra and the Holter monitor may result in duplicate ventricular event markers to be transmitted. This would result in multiple entries in the ventricular event spreadsheet with a non-physiological time between the ventricular events. Therefore, ventricular events occurring within 100 ms of a previous ventricular event will be discarded as they are non-physiological (e.g. correspond to a rate exceeding 600 bpm).

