For each long interval event identified above, the surface ECG signals and EGM will be manually reviewed to determine if they are true pauses or due to telemetry dropout. For any true pauses, the surface ECG signal, accelerometer signal, and device markers will be examined to determine if the pause was related to the MARVEL 2 algorithm or for another reason (e.g. R-wave undersensing).

Similarly, for each high heart rate event, the surface ECG, the accelerometer signal, and MARVEL 2 markers will be examined to determine if the high heart rates were induced by MARVEL 2 algorithm oversensing or for some other reason (e.g. appropriate rate response, T-wave oversensing). Subjects free from pauses and oversensing induced tachycardia exceeding 3 minutes related to the MARVEL 2 algorithm will be considered to have met the primary safety endpoint.

An exact binomial test will be used to test the primary safety hypothesis. Specifically, the numerator will be the number of subjects meeting the primary safety endpoint. The denominator will be the number of subjects with Holter recordings with usable telemetry while the MARVEL 2 algorithm is downloaded.

[REDACTED]

The following pre-specified subgroups will be evaluated if there are two or more subjects who do not meet the primary safety objective: sex, geography (US versus outside of US), and predominant heart rhythm during Holter recording (normal sinus node function and persistent 3rd degree AV block, intact

AV conduction, or other predominant rhythm). Fisher's exact test will be used to identify differences between subgroups.

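### Both primary safety screens give the telemetry-dropout flag a label that names two different columns (4 = D, K = 11), and the readable SAP does not show which is meant

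*SAP*

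**What the plan says.** The primary safety endpoint (SAP 7.5.4.1) has two components: freedom from software-related pauses longer than two cardiac cycles, and freedom from oversensing induced tachycardia above 100 bpm lasting more than 3 minutes. SAP 7.5.4.4 finds candidate events in the ventricular event spreadsheet, whose description it refers to section 7.5.2.4. Three rules matter here.

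- Pause screen. The V-V interval must exceed twice the lower rate interval, and if "there is no telemetry dropout (i.e. column 4 (K) = 0) the event will be flagged for further investigation".
- High-rate screen. For events with "evidence of telemetry dropout (i.e. column 4 (K) = 1) will not be computed", the rate is left out and the event is ignored when the duration above 100 bpm is added up.
- Manual review. It starts from the output of the pause screen: "For each long interval event identified above, the surface ECG signals and EGM will be manually reviewed".

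Protocol 17.6.4 describes the pause search differently. Ventricular markers are searched for long intervals, and manual review of the surface ECG then separates true pauses from dropout. It states no dropout filter ahead of that review.

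**The concern.** In a spreadsheet, column 4 is D and K is column 11. A programmer who follows the number and one who follows the letter read different variables, and the label is used in both screens of a primary endpoint.

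In the pause screen the two possible errors differ in their effect. If the wrong column lets dropout intervals through, manual review can still sort them out and the cost is reading time. If it removes real long intervals, they never reach the SAP's review step, and the subject is scored as free of pauses. That error favours the device. It could also go unnoticed, because SAP 7.5.4.5 expects all subjects to meet the endpoint and an empty list of flagged pauses would look normal.

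The high-rate screen can fail in the same direction. At a rate just above 100 bpm the interval is just under 60/100 = 0.6 s. One lost marker doubles it to just under 1.2 s, an apparent rate just over 60/1.2 = 50 bpm. If that event is not recognised as dropout, it can break a fast run and keep it under 3 minutes.

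Under SAP 7.1.3 the study succeeds only if the safety null hypothesis is rejected along with the efficacy one.

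**Working it through.** **Step 1: is this a different labelling convention?** Each readable number-letter pair in the SAP was compared with the letter's place in the alphabet.

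| SAP section | Spreadsheet | Labels | Agree? |
|---|---|---|---|
| 7.5.3.4 | accuracy | 1 (A), 2 (B), 11 (K), 12 (L), 13 (M), 14 (N), 15 (O), 17 (Q) | yes, all 8 |
| 7.5.4.4 | ventricular event | 3 (C), 6 (F) | yes, both |
| 7.5.4.4 | ventricular event | 4 (K), used twice | no: 4 = D, K = 11 |

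The same section, on the same file, has "column 6 (F) in the ventricular event spreadsheet has the values 5, 6, 7, or 14", which pairs correctly. The accuracy spreadsheet pairs K with 11: "columns 11 (K) and 12 (L) indicate auto setup phase". Its own dropout rule is also consistent: "column 13 (M) = 0 and column 14 (N) = 1". The accuracy spreadsheet is a different file, so these labels confirm the convention but do not show which column of the ventricular event file holds dropout.

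**Step 2: the plan's own safety figures.** Inputs from SAP 7.5.4.3 and 7.5.4.5: n = 70, goal 87%, one-sided alpha 0.025, assumed true rate 98%. The exact lower limit for r passes is the 0.025 quantile of Beta(r, 70 - r + 1).

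- 67 of 70: lower limit 87.98%, above 87%, passes.
- 66 of 70: lower limit 86.01%, fails. So 67 is the correct minimum.
- 70 of 70: lower limit 0.025^(1/70) = 94.87%, which rounds to the stated 94.9%.
- P(X >= 67) at a true rate of 87% is 0.0145, within 0.025. At 98% it is 0.948, above the stated 90%.

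All of the plan's figures reproduce. None depends on the label.

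**Step 3: what missed failures would do.** The documents give no figure for the share of failing subjects that a wrong column would miss. Call it s, as an assumption. With true pass rate p, the apparent pass rate is p_obs = 1 - (1 - p)(1 - s). At p = 87%:

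| s (assumed) | p_obs | P(at least 67 of 70) |
|---|---|---|
| 0 | 1 - 0.13 x 1 = 0.8700 | 0.0145 |
| 0.25 | 1 - 0.13 x 0.75 = 0.9025 | 0.080 |
| 0.50 | 1 - 0.13 x 0.50 = 0.9350 | 0.325 |
| 0.75 | 1 - 0.13 x 0.25 = 0.9675 | 0.807 |
| 1 | 1 - 0.13 x 0 = 1 | 1.000 |

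This is a range, not an estimate. The label error could correspond to s = 0.

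**Step 4: what s = 1 would need.** Take a constructed file of 1,000 events at a lower rate of 50 bpm. The threshold is 2 x 60/50 = 2.4 s, and ten intervals of 2.6 s exceed it. Let column K be 0 throughout and let column D hold only 1 or 2. Filtering on K = 0 flags 10 intervals; filtering on D = 0 flags none. The result follows entirely from the values placed in D, about which the readable text says nothing. If instead D is the dropout flag, the number is right and following the letter is the error.

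**The case against.** The strongest reply is that this is a slip in a cell reference and no more. The SAP states the condition in words as well: dropout absent in one screen, present in the other, coded 0 and 1. A programmer with the full SAP can look up the layout in 7.5.2.4; its redaction in the public copy is not a gap in the plan. There are other looks at the data too. SAP 7.5.1 has experienced sponsor staff review every Holter dataset and confirm correct feature operation. SAP 7.5.4.7 requires the proportion of beats with dropout to be computed, which could expose a wrong column if it draws on the same flag (the SAP does not say). The one-subject margin between 67 and 66 belongs to any exact threshold and does not measure this slip.

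Much of that stands. It rules out two stronger readings that a reader might infer.

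- That the number is the wrong half, so that reading column 4 gives the wrong variable. No readable text says what column D or column K of this file holds, so the letter could equally be the slip.
- That every pause would go unflagged. This needs a read by position, a column D that is not the dropout flag and is never 0 at a long interval, and no later detection. None of these is documented.

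What the reply does not remove is that an operative endpoint rule contradicts itself in two places. The words say what the flag means but not where it is. The general Holter review is not tied to the endpoint rule, and the SAP's pause review sees only what the screen passes on.

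**Conclusion.** The label error is certain: column 4 (K) names two columns, it appears in both primary safety screens, and it is the only mismatch among the readable labels. One of the two literal readings must therefore take the wrong variable. Which one cannot be told from the readable text.

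The consequence is uncertain. If the programmer resolves the label correctly, nothing changes. If not, intervals could be wrongly dropped or kept before manual review, and the step 3 figures show how the chance of passing at a true rate of 87% would move under assumed shares of missed failures. The top of that range is hypothetical. It also requires that no subject fails on the tachycardia component, or that those failures are missed as well.

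The design is untouched: the sample size of 70, the alpha of 0.025, the power and the threshold of 67 all stand. The correction is worth making because it is nearly free and concerns a primary endpoint.

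**What to change.** 1. In SAP 7.5.4.4, correct both references against the layout in 7.5.2.4, and cite the flag by variable name as well as by number and letter.
2. Before the screens run, confirm that the column read is the dropout flag, by its header or against the layout. Checking only that it holds 0 and 1 is not enough, because another 0/1 column would pass.
3. Send every V-V interval longer than twice the lower rate interval to manual ECG review, as Protocol 17.6.4 describes, and keep the dropout flag as information for the reviewer. The pause component then no longer depends on the flag. The high-rate screen still does, so items 1 and 2 remain necessary.

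The cost is a two-place text correction, a short programming check and some additional intervals to read. No sample size, alpha, power or pass threshold changes.

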
Study Design
	
The MARVEL 2 study is an acute, prospective, global, multi-center, software-download clinical study. The study is planned to be conducted in US, Europe, and Asia. The study is expected to be conducted at approximately 15-20 centers in up to 100 subjects to obtain at least 70 usable Holter datasets to meet the objectives of the study. The expected total study duration (from first subject enrollment to the exit of the last subject) is approximately 6-months; this represents the time necessary to enroll the target sample size of at least 70 subjects with usable Holter datasets. Software will be downloaded into patients implanted with a Micra device to allow the new algorithm performance to be measured in patients where a Micra device has already been chosen as most appropriate for the patient.
 
Most enrolled subjects will complete the study procedures during a single study visit. However, subjects enrolling in the study at the time of their Micra implant (anticipated to be approximately 10 subjects) will have the investigational algorithm downloaded following Micra implant, prior to hospital discharge, and approximately 1-month post-implant. This subset of subjects with de novo Micra implants will allow the MARVEL 2 features to be tested at multiple points in the device life cycle.
 
Since the download algorithm running in a Micra device significantly increases current drain, a 2-4 hour acute study is used to limit the reduction in device longevity.

Sample Size
	
A sample size of at least 70 subjects with usable Holter datasets following MARVEL 2 software download is required to test the study's primary objectives. This includes at least 35 subjects with a predominant heart rhythm of normal sinus node function and persistent 3rd degree AV block to provide at least 90% power to test the study's primary efficacy objective. Since all subjects may not have usable Holter data, up to 100 subjects may be enrolled to achieve the goal of 70 usable Holter datasets. Enrollment may end once the target number of usable Holter datasets has been obtained.

	
There is no minimum number of subjects required to be enrolled at a center. However, to ensure a widespread distribution of data and minimize center bias in study results, the maximum number of enrolled subjects at a single site is 20.

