15.1 Adverse Event and Device Deficiency Assessment

15.1.1 Adverse Events

All Adverse Events (AEs) regardless of their severity or relationship to the Micra implant procedure, MARVEL 2 features, or study procedures will be collected throughout a subject's participation, starting from the time the informed consent form is signed. Reporting of these events to Medtronic will occur on an AE Form, including event description, date of AE, treatment, resolution, assessment of both the seriousness of the AE and the relatedness to the system components. Each AE must be recorded on a separate AE e-CRF. Documented pre-existing conditions are not considered AEs unless the nature or severity of the condition has worsened. In addition, AEs impacting users or other persons, Non-subject Adverse Events, (reportable per ISO 14155) will be collected.

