7.5.4.3 Performance Requirements

The percentage of subjects meeting the primary safety endpoint is significantly greater than 87% (i.e. the lower two-sided 95% confidence interval for the estimate exceeds 87%). For example, in a sample size of 70 subjects with usable Holter datasets, this objective would be met if at least 67 of the 70 subjects (96%) meet the primary safety endpoint. Further, with a sample size of 70 subjects with usable Holter datasets the lower two-sided 95% confidence interval will be 94.9% if all 70 subjects meet the primary safety objective.

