7.5.4.5 Sample Size Calculation

A sample size of 70 subjects with usable Holter telemetry data during the MARVEL 2 study procedures provides at least 90% power to test the primary safety hypothesis given the following assumptions:

1. One-sided type I error rate = 0.025
2. Single test of a proportion after all enrolled subjects have had an opportunity to complete the MARVEL 2 study procedures and have had their Holter data evaluated.
3. The proportion of subjects meeting the primary endpoint in the MARVEL 2 pacing mode will exceed 98%.

Justification of Sample Size Assumptions

It is expected that all (100%) subjects will meet the primary safety endpoint. Specifically, in the MARVEL study, no pauses exceeding two cardiac cycles (as defined by the lower pacing rate interval) and no oversensing induced tachycardia exceeding three minutes were observed.

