7.5.4.7 Missing Data and Sensitivity Analyses

The primary source of missing data for this objective is anticipated to be Holter usability status and telemetry dropout during MARVEL adaptive mode pacing. Note that both sources of missing data can plausibly be assumed independent of primary safety endpoint status as Holter usability status is primarily related to electrode contact. However, to quantify the amount of missing data, the number of unusable Holter files and the proportion of beats during MARVEL 2 operation with telemetry dropout will be computed.

If Holter data from subjects who had the MARVEL 2 software downloaded is missing (e.g. deemed entirely unusable, Holter never placed on subject), it will be included in a tipping point analysis to determine the sensitivity of the statistical inference to the missing data. If the tipping point is less than the number of subjects with missing data, stochastic methods may be employed to aid in interpreting the likelihood the tipping would be achieved. Specifically, simulations from a Beta distribution with shape parameters based on the observed data will be used to compute the predictive probability of observing or exceeding the tipping point.

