7.5.5.6 Determination of Subjects/Data for Analysis

All subjects with normal sinus node function and persistent 3rd degree AV block during Holter monitoring and with paired LVOT VTI measurements during MARVEL 2 adaptive pacing and VVI pacing will be included in the analysis. Note that as long as a subject’s predominant rhythm can be determined from the Holter recording, the subject may be included in this analysis as determination of predominant rhythm does not require device marker channel.

For *de novo* subjects, only echocardiogram data collected at the pre-hospital discharge visit will contribute to the analysis of the secondary objective. However, if a *de novo* subject is missing paired

echocardiogram on the day following their Micra procedure but have paired LVOT VTI data from their 1-month visit, the 1-month data will be used in the analysis if available.

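### In the readable text, a Holter-wearing subject with a documented software-related safety event but unreadable telemetry is left out of the primary safety test and treated as missing

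*SAP*

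**What the plan says.** SAP 7.5.4.1 (and Protocol 8.2.1.2) defines success as freedom from two kinds of MARVEL 2 software-related event: pauses longer than two lower-rate intervals, and accelerometer oversensing that drives the rate above 100 bpm for more than 3 minutes. The window is the entire Holter monitoring period with the features enabled. The Safety Assessments row of the protocol synopsis says that all Holter recordings will be evaluated for pauses and oversensing-induced tachyarrhythmia. It sets no usability condition.

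The test population is narrower. SAP 7.5.4.4 states: "The denominator will be the number of subjects with Holter recordings with usable telemetry while the MARVEL 2 algorithm is downloaded". SAP 7.5.4.6 likewise admits only recordings with usable telemetry, and SAP 7.1.4 defines usable by a visible device and algorithm marker channel. Candidate events are found by searching the ventricular markers.

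SAP 7.5.4.7 sends a subject who received the download but has no usable Holter data to a tipping-point analysis, optionally followed by a Beta simulation based on the observed data. Its premise is that "both sources of missing data can plausibly be assumed independent of primary safety endpoint status".

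Events can be documented in other ways. The Holter also records surface ECG. Protocol 15.1.1 says "All Adverse Events (AEs) regardless of their severity or relationship to the Micra implant procedure, MARVEL 2 features, or study procedures will be collected", and Protocol 15.3.1 (Table 6) has the investigator and the sponsor classify relatedness to the MARVEL 2 software.

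**The concern.** The endpoint window and the test denominator do not match. A qualifying event in a subject who wore the Holter with unreadable telemetry lies inside the endpoint of SAP 7.5.4.1 and outside the test of SAP 7.5.4.4. If that event is documented and attributed to the software, the outcome is known, yet the readable rules handle it as unknown.

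The independence premise does not help here, because it concerns subjects whose status is unobserved. It is also not fully secure. Protocol Table 4 lets the clinician discontinue MARVEL 2 in a symptomatic subject, and Protocol 13.13 foresees withdrawal for problems of software safety or performance. Either could link an event to a short or absent usable recording.

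At stake is one of two primary hypotheses that must both be rejected, in a single-arm comparison that tolerates only three failures in 70.

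**Working it through.** **Inputs.**
- Performance goal: 87%, met if "the lower two-sided 95% confidence interval for the estimate exceeds 87" per cent (SAP 7.5.4.3).
- "One-sided type I error rate = 0.025", n = 70 and assumed success 98% (SAP 7.5.4.5).
- Exact binomial test (SAP 7.5.4.4).

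**Formulas.** For x successes in n, the one-sided p-value is the sum over k = x to n of C(n,k) × 0.87^k × 0.13^(n−k). The exact lower limit is the 0.025 quantile of Beta(x, n − x + 1).

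**The plan's own figures reproduce.**
- 67/70: p = 0.0145, lower limit 87.98%, met.
- 66/70: p = 0.0412, lower limit 86.01%, not met. So 67 is the minimum, as stated.
- 70/70: lower limit 94.87%, stated as 94.9%.
- Power at 98% success: 94.8%. This agrees with "A sample size of 70 subjects with usable Holter telemetry data during the MARVEL 2 study procedures provides at least 90% power".

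**Effect of adding known failures.** Each one adds 1 to n and nothing to x.

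| Usable-telemetry result | p | Lower limit | Added failures that reverse it | Result then | p | Lower limit |
|---|---|---|---|---|---|---|
| 67/70 | 0.0145 | 87.98% | 1 | 67/71 | 0.0377 | 86.20% |
| 68/70 | 0.0038 | 90.06% | 2 | 68/72 | 0.0345 | 86.38% |
| 69/70 | 0.0007 | 92.30% | 3 | 69/73 | 0.0316 | 86.56% |
| 70/70 | 0.00006 | 94.87% | 4 | 70/74 | 0.0288 | 86.73% |

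With one fewer added failure the goal is still met in every row; for example, 68/71 gives p = 0.0131. The boundary behaviour is not special to n = 70. For usable n from 70 to 99, a result at the maximum allowed number of failures is reversed by one more at 27 of 30 values (the exceptions are 75, 86 and 96).

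**How likely the boundary is.** P(exactly 67/70) = C(70,3) × p^67 × (1−p)^3. At the plan's 98% this is 11.3%. As a range of assumptions, it is 2.8% at 99%, 19.2% at 97% and 22.0% at 95%.

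**Joint chance of a one-case reversal at 67/70.** The documents give no count of exposed subjects without telemetry. Assume m of them, each with the same 2% event rate and any event documented: 0.113 × (1 − 0.98^m). This gives 0.7% for m = 3, 1.1% for m = 5 and 2.1% for m = 10.

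**The Beta simulation.** If its shape parameters are the observed counts (an assumption; the SAP says only that they rest on the observed data), then at 67/70 a missing subject is drawn as a failure about 3/70 = 4.3% of the time. A documented failure would thus be simulated mostly as a success.

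**The case against.** The strongest reply is that an event without telemetry is hard to call a known failure. SAP 7.5.4.4 attributes events by reading surface ECG together with the accelerometer signal and MARVEL 2 markers, and those arrive by telemetry. SAP 7.5.5.6 does accept recordings without markers, because "determination of predominant rhythm does not require device marker channel", but attributing an event to the algorithm asks for more than classifying rhythm. This stands as a limit: only events judged software-related should count, and the judgement is less certain. Protocol 16.1 also justifies having no event committee because the endpoints are objective Holter criteria, and form-based relatedness weakens that argument.

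Second, counting telemetry-free subjects only when they fail makes the denominator depend on outcome. From 67/71, adding five event-free subjects gives 72/76 (lower limit 87.07%, met). With 30 added subjects and one event, 96/100 has a lower limit of 90.1%. A reader might infer that the present rule demonstrably biases the pass rate upward. The documents do not show that, since it requires excluded subjects to fail more often than included ones.

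Third, the matter is partly handled. At 67/70 the tipping point would be reported as one, and adverse events are summarized separately. But neither sets the primary decision.

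Three further inferences fail:
- That up to 30% of subjects could be affected. The synopsis says "up to 100 subjects may be enrolled to achieve the goal of 70 usable Holter datasets", but this is an enrolment ceiling. Enrolment occurs at consent, so the gap includes subjects never exposed, and enrolment may stop early.
- That programmer ECG strips will be available. Protocol 13.7.11 says that a cable is connected; it sets no duration and requires no recording.
- That every exposed subject with an event is wrongly dropped. For a subject never fitted with a Holter, the event is outside the endpoint as worded.

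**Conclusion.** The gap holds in the readable text for one defined group: subjects who wore the Holter with the features enabled, had no usable telemetry, and have a documented qualifying event judged software-related. Following the stated rules leaves them out of the primary test, which also sits badly with the synopsis commitment to evaluate all Holter recordings.

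A reader might infer that one such case would generally overturn the result. It would do so only with three failures already observed among 70. At 70/70, which the sponsor expects because the earlier MARVEL study saw no qualifying event, four are needed. The number of such subjects is unknown and may be zero.

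The conclusion assumes that no rule sits in the redacted block after the denominator sentence or in the largely redacted SAP 7.5.2. None appears in the readable parts of SAP 7.5.4 or Protocol 17.6. The practical risk is small, but a pivotal safety test should not leave the scoring of a documented failure open.

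**What to change.** **SAP 7.5.4.4 and 7.5.4.6.** State that a subject who wore the Holter with the MARVEL 2 features enabled, and who has a qualifying pause or oversensing-induced tachycardia in that period documented on the Holter surface ECG or on an adverse event or device deficiency form and judged related to the MARVEL 2 software, is counted in the denominator as not meeting the endpoint, whatever the telemetry status. Say whose relatedness classification governs if investigator and sponsor differ. Name the source for enabled status as well: the SAP reads it from the ventricular event spreadsheet, so the procedure worksheet would have to supply it here.

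**SAP 7.5.4.7.** Fix such subjects as failures before the tipping-point and Beta steps. Keep only subjects of unknown status as missing.

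**Reporting.** Give the primary safety result with and without these subjects, and the number of Holter-wearing exposed subjects without usable telemetry. Events in subjects never fitted with a Holter stay in the adverse event summary unless the endpoint wording is changed.

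**Cost.** SAP wording, and a cross-check of records already collected for a few subjects. No study procedure changes. The drawback to state openly is that telemetry-free subjects enter only if they fail, so the estimate is conservative, and attribution without markers is less certain. If no such subject exists, the result is unchanged.
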